2. STUDY DESIGN

2.1. Overview

This is a single center, randomized & controlled trial comparing the efficacy of the Propel mini or contour stent vs. Nasopore impregnated with triamcinolone acetonide at reducing frontal sinus opening stenosis and polypoid edema after ESS in patients with CRS with polyposis. Eligible subjects who undergo standard of care bilateral frontal sinusotomy will have each frontal sinus randomly assigned to either a Propel steroid eluting stent or a Nasopore nasal dressing impregnated with 2.5 ml of triamcinolone acetonide 40 mg/ml. The specific Propel stent will be chosen based on the shape of frontal sinus opening and best fit as decided by the operating surgeon. Patients will be reassessed on approximately post-operative day 7, 14, 30, 90 days, 6 months, and 12 months at their SOC follow-up visits. On the day 14 visit, the frontal sinus Propel stent and Nasopore will be completely removed per SOC. Video will be taken of the frontal sinus opening, and assessed for scarring/adhesions, presence of polypoid edema, frontal sinus patency, need for oral steroids or other interventions. Additionally, endoscopic scoring of frontal sinus by the above measures will be evaluated by 2 independent sinus surgeon reviewers. The reviewers will also be asked to rank the two frontal sinus openings as better, same or worse, compared to the opposite side.

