will have standard post-operative visits at approximately 1 week, 2 weeks, 30 days, 90 days, 6 months and 12 months. On post-operative day 14 the first endoscopic evaluation of the frontal sinus opening after implant removal will be performed. Video is routinely recorded and this will be copied for the study, edited to remove any identifying features of the subjects, for review and scoring by qualified independent reviewers. If at any of the post-operative visits oral steroids, antibiotics or in-office procedures is deemed medically necessary this will be allowed and recorded as part of the study results. Subjects' participation will conclude at the 12 month visit.

Schedule of Activities (R Research/SOC Standard of Care)

Visit	0 (Screening)	Operative Visit	FUV 1	FUV 2	FUV 3	FUV 4	FUV 5	FUV 6
Visit timing	Up to 90 days pre-operative	Day 0	1 week post op (+/-3 days)	2 weeks (+/-5 days)	1 month (28 to 56 days post op)	3 months (+/-14 days)	6 months (+/-21 days)	12 months (+/-21 days)
Obtain informed consent/confirm eligibility (R)	X							
Medical and sinonasal history evaluated (SOC)	X							
Bilateral endoscopic sinus surgery (SOC)		X						
Confirm eligibility/ Randomize treatment (R)		X						
Placement of frontal sinus opening treatments (SOC)		X						
Obtain validated SOC sinonasal symptom and quality of life questionnaires (SOC)	X		X	X	X	X	X	X
Complete ENT and sinonasal exam including rigid endoscopy (SOC)	X		X	X	X	X	X	X
Rigid endoscopy with documentation (SOC)	X	X	X	X	X	X	X	X
Abstraction from endoscopy record on frontal sinus opening scarring, polypoid edema,				X	X	X	X	X

overall condition for data analysis and external review (R)								
Adverse event review (R)			X	X	X	X	X	X

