5.1. Efficacy Assessments

Efficacy will be determined by comparing the right and left frontal sinus opening after removal of the stent and dressing on POD 14, and then around day 30, 90, 6 month and 12 months. The frontal sinus opening will be assessed with a rigid endoscope, using 30, 45 and/or 70 degree scopes as necessary. Our primary efficacy outcome will be a grade assigned by 2 blinded, independent sinus surgeon experts as: better, worse or same, comparing overall appearance of the study subject's frontal sinus openings after implant removal.

Additionally, the frontal sinus opening will also be graded on an adhesion/scarring scale, a polypoid edema scale, size in mm of the opening as measured by a visual analog scale/comparison to 4 mm suction, and visualization of the roof of the frontal sinus.

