11.2. Sample Size Determination

Sample size is based on a non-inferiority design. Based on historical data it can be estimated that frontal sinusotomy will have a patency (success) rate of 85%. Given the lack of any known evidence to the contrary, we will assume that both the Propel mini/contour stent and the Nasopore impregnated with 2.5 mls of Kenalog 40 mg/ml placed in the FSO after ESS will result in a patency rate of 85%. Given that all prior clinical trials investigating local delivery of steroid to the FSO have utilized the Propel mini or contour stent, this will serve as our “standard therapy” group. Using an $\alpha= 0.05$, Power= 80%, and a minimum significant difference (δ) of 25%, 28 patients (56 total frontal sinus interventions) will be enrolled to be 80% sure that the upper limit of a one-sided 95% confidence interval will exclude a difference in favor of the “standard therapy” group of more than 25%. The ESS surgical procedure typically has a 1% complication rate and frontal sinusotomy failure rate of approximately 5%. Thus by ensuring subjects meet inclusion criteria a) through d) and that none of the exclusion criteria apply prior to enrollment, we would have a very low rate of screen failure, where an enrolled subject does not ultimately meet inclusion criteria e) and f). Hence enrolling 30 subjects should be sufficient to reach our statistical needs.

[figure not shown]
11.3. Planned Statistical Analysis:

Primary outcome measure: Grading by a blinded independent sinus expert as to whether the the propel sinus stent frontal sinusotomy side is better, worse or the same.

[figure not shown]
Secondary outcome measures:

1. Mucosal/polypoid edema
2. Adhesion/scarring
3. Size of frontal sinus opening
4. Visualization of the frontal sinus roof
5. Need for post-operative oral steroids
6. Need for post-operative interventions beyond normal debridement

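### Does the plan need to change because it does not say whether secondary outcome 5, post-operative oral steroids, is counted per sinus opening or per patient?

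*Combined protocol and SAP*

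**What the plan says.** Section 11.3 names "Need for post-operative oral steroids" as secondary outcome 5. The readable text gives it no unit, time window, source or test. The other five secondary outcomes are listed just as briefly.

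Other places bear on what it means:

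- **Section 2.1 (Overview)** has the opening filmed and "assessed for scarring/adhesions, presence of polypoid edema, frontal sinus patency, need for oral steroids or other interventions". It then says that "endoscopic scoring of frontal sinus by the above measures will be evaluated by 2 independent sinus surgeon reviewers".
- **Section 5 (Methods and Study Procedures)** says that if at any post-operative visit "oral steroids, antibiotics or in-office procedures is deemed medically necessary this will be allowed and recorded as part of the study results". It names no side.
- **Schedule of Activities** has a row that begins "Abstraction from endoscopy record on frontal sinus opening scarring, polypoid edema" and continues with overall condition, for analysis and external review. Oral steroids are not in that row.
- **Section 5.1 (Efficacy Assessments)** states "Efficacy will be determined by comparing the right and left frontal sinus opening after removal of the stent and dressing on POD 14", with later time points to follow. It adds that "the frontal sinus opening will also be graded on an adhesion/scarring scale, a polypoid edema scale, size in mm of the opening", together with visualization of the sinus roof. Oral steroids are not among these grades.
- **Section 11.2** counts sinuses as well as patients: "28 patients (56 total frontal sinus interventions) will be enrolled". Section 3.1 plans 30 patients and 60 sinusotomies.

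**The concern.** The design is within-patient. Section 7.4 puts one treatment on the left and the other on the right in every patient, so there is no separate group of stent patients to set against dressing patients. The only efficacy contrast the plan describes is one side against the other.

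A course of oral steroids is systemic and reaches both sinuses. If outcome 5 is the visit record and no side is attached, each patient contributes one value, and that value says nothing about which treatment did better. Placed in a left-right table, every course counts once for the stent and once for the dressing, and the difference is zero whatever the treatments do.

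This would matter because the sample size rests on non-inferiority, where no difference is the favourable result. A tie produced by the way the data were laid out could be read as evidence that the two treatments lead to equal need for steroids. The per-opening reading of section 2.1 can differ between sides. So the choice of source decides what the outcome can show, and section 11.3 does not visibly make that choice.

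**Working it through.** **1. The plan's own figure.** The documents give no calculation for outcome 5. The only figure is the sample size for patency in section 11.2: 85% on both treatments, margin 25 points, one-sided 5%, power 80%.

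n per treatment = 2 × 0.85 × 0.15 × (1.645 + 0.842)² / 0.25² = 25.2, so 26.

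The plan states 28. Allowing for a 5% loss gives 26 / 0.95 = 27.4, so 28. The figure is reproduced closely enough, and it does not depend on outcome 5.

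**2. The tie.** Let x be 1 if a patient has a recorded course and 0 if not. With no side recorded, stent side = x and dressing side = x. In every patient the difference is x − x = 0. Discordant pairs are 0 and the mean difference is 0, at 28 or 30 patients and at any rate of use. This needs no assumed rate.

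**3. How misleading the tie could look.** Suppose someone also analysed the two sides as independent groups with the same proportion p. The one-sided 95% upper limit would be 1.645 × √(2p(1 − p)/n), which is largest at p = 0.5:

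- n = 28: 1.645 × √(0.5/28) = 0.220
- n = 30: 1.645 × √(0.5/30) = 0.212

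Both lie below 0.25, so the margin would be met automatically. Reaching that result takes three steps: copying each patient's value to both sides, ignoring the pairing, and applying the patency margin to a steroid outcome. The plan specifies none of them for this outcome.

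**4. If a side is recorded.** Discordant pairs become possible and the standard paired analysis applies. An exact two-sided McNemar test with all m discordant pairs in one direction has p = 2 × 0.5^m. That is 0.0625 for m = 5 and 0.031 for m = 6, so at least six one-way pairs are needed.

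**5. Which reading the text supports.** Setting the section 11.3 list beside the sections that say what is collected:

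| Secondary outcome | Graded per opening in 5.1 | Visit record in section 5 |
|---|---|---|
| 1 Edema | yes | no |
| 2 Adhesion/scarring | yes | no |
| 3 Size of opening | yes | no |
| 4 Roof visualization | yes | no |
| 5 Oral steroids | no | yes |
| 6 Further interventions | no | yes (in-office procedures) |

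Outcomes 1 to 4 match the per-opening grades one for one. Outcomes 5 and 6 match the visit record. The schedule's abstraction row also leaves steroids out. The per-opening reading of outcome 5 rests on the overview in section 2.1, where scoring by the measures just listed can reasonably mean those that can be seen on endoscopy.

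**6. Scheduled use.** Section 5 separates the planned peri-operative course, which ends at the first post-operative visit, from steroids judged necessary at a post-operative visit. The second is what is recorded as a result, so the natural count does not mix the two.

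**The case for a change.** The strongest case for a change runs as follows. Two sections describe the item differently. The left-right contrast is the only efficacy comparison the plan states. The outcome list does not set item 5 apart from items 1 to 4. Under one of the two sources, that contrast is zero by construction. A sentence or two would settle the matter, and it is easier to settle before the videos are scored, because a per-opening rating not collected then would need a second review. The videos are already labelled by side (section 9) and the reviewers are already planned, so the cost is small.

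Much of this stands. The unit is not stated in the readable text, and a record without a side cannot separate stent from dressing. Three parts do not carry over into a needed change:

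- **The record is not shown to lack a side.** Section 5 does not mention side, but the same sentence covers in-office procedures, which may well be done on one side. Its silence therefore does not fix the unit. The data collection forms mentioned in section 11.1 are not in the documents.
- **The harmful analysis is not planned.** It has to be supplied by the reader, as step 3 of the working shows.
- **A per-side rating is not clearly better.** A reviewer's judgement of steroid need for each opening would overlap with the polypoid edema grade. After any course it would reflect a treatment that both sides had received. With 30 patients, discordant pairs may also be few. Whether to have it is a matter of preference.

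**Conclusion.** This is a gap in detail that a competent analyst fills sensibly, and the plan can stand. Both available readings are sound. Courses recorded without a side are a valid description per patient. A judgement made per opening, or a course recorded with the side that prompted it, is ordinary paired binary data. No analyst would sensibly test a systemic treatment duplicated across two sides of the same patient.

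The only firm size is conditional: if no side is recorded and the value is copied to both sides, the difference is 0 in all 28 to 30 patients. The effect is confined to one of six secondary outcomes. The primary better/same/worse grade, secondary outcomes 1 to 4 and the 28-patient calculation do not use it.

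The conclusion assumes that outcome 5 comes from the visit record, as the match between sections 5, 5.1 and 11.3 suggests, and that the results are reported per patient unless a side was recorded. It covers only the readable text, since the figures near section 11.3 are not shown. Stating the unit would be a courtesy to readers of the results; the inference does not depend on it.

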Appendix 1 – Images- Propel mini stent

Appendix 2- Images- Propel contour stent

[figure not shown]
Appendix 3 – Images- Nasopore

[figure not shown]
